4 STUDY DESIGN

4.1 OVERALL DESIGN

This is a first human, single-center, dose escalation, open-label trial of a single application of topically delivered NB01 in subjects with moderate, non-cyclical facial acne.

Ten subjects will be assigned to 1 of 2 dose cohorts in a stepwise fashion after a 5-day pre-treatment with 5.0% daily BPO gel (<https://www.perrigo.com/business/product.aspx?ID=88&let=B> Perrigo 5% BP Aqueous Gel).

- Cohort 1: 10⁵ CFU/cm² NB01
- Cohort 2: 10⁶ CFU/cm² NB01

This will be ascending dose finding whereby 5 initial subjects will be assigned to Cohort 1 to receive a single application of 10^5 CFU/cm² to the facial skin of the nose/cheek. If there are less than 2 dose-limiting toxicities (DLTs) during the 7-day safety assessment, a Dose Escalation Meeting will be held between the PI and the Sponsor Medical Monitor to determine whether Cohort 2 will be opened to enrollment.

4.2 SCIENTIFIC RATIONALE FOR STUDY DESIGN

Acne vulgaris is a multifactorial disease caused by overgrowth of *P. acnes*, impaction of hair follicles, excessive sebum production and hormonal dysregulation. Recent literature from the Human Microbiome Project has shown there are unique *P. acnes* microbial signatures specific to healthy and acne disease states (Fitz-Gibbon et al. 2013), (Tomida et al. 2013). Subsequent literature discovered a repressor in the porphyrin pathway in health-associated strains resulting in significantly lower porphyrin production (Johnson et al. 2016). Porphyrin is a known inflammatory mediator in acne pathogenesis (Kang et al. 2015). Porphyrin levels inversely correlate with therapeutic improvement in acne (Richter et al. 2016). Additional papers have highlighted other virulent factors such as the pIMPLE plasmid that may be associated with acne pathogenesis and were found to be more common in disease-associated strains (Kasimatis et al. 2013).

From this data, we hypothesize that by eliminating resident disease-associated bacterial strains and replacing them with a health-associated *P. acnes* transplant, we may be able to improve, mitigate, treat clinical disease (acne) and prevent recurrences/flare-ups of said disease. Instead of current approaches which focus on eliminating all bacteria from the skin, we aim to deliver healthy bacteria to restore the skin to a healthy state via this replacement therapy.

We aim to test this in a Phase Ib single application study evaluating the safety, tolerability, and clinical impact that a single application of NB01 has on adult subjects with moderate acne. We want to profile the change in microbiome over the course of therapy to determine if exogenously delivered bacteria can populate the skin (engraftment) and cause a shift in the microbiome safely and subsequently impact acne biomarkers (porphyrin) that may correlate with clinical disease. Health-associated *P. acnes* contain both deoR and Cas5, thus the ratios of deoR/PanBac and Cas5/PanBac is approximately 1 in our formulation. Disease associated *P. acnes* typically lack deoR and Cas 5 (Kang et al, 2016) leading to a deoR/PanBac <10% on acne individuals. We expect an upwards shift in deoR/PanBac and Cas5/Panbac with the application of our strains to acne subjects. Thus, engraftment is defined as deoR/PanBac>40% and Cas5/PanBac>40%. This will help to determine dosing regimen/schedule for multi-dosed trials where the drug will be applied in a frequency to ensure that product levels remain above these parameters. For example, if deoR/PanBac drops to <40% at or before 6 hours then the application will be BID (Q12 hours). Disease-associated strains, in contrast, typically lack deoR and Cas4, but contain transposase2 (TPase2). Subjects will also be profiled with TPase2/PanBac ratios to determine how the pathogenic strain profiles are impacted over time with application of drug, and if there are certain profiles that increase or decrease likelihood of successful engraftment.

Engraftment measurements would be more challenging to obtain in healthy individuals in which we would be trying to replace a healthy microbiome with a healthy microbiome. Our product is low risk, using bacteria native not only to human skin, but to the pilosebaceous units of the face, and *P. acnes* makes up 90% of the bacteria on the skin in both diseased and healthy individuals (Fitz-Gibbon et al. 2013).

We intend for this therapy to eventually be used in all ages of acne subjects ranging from 13-40, and all disease severities as either monotherapy for mild to mild/moderate acne and as an adjuvant therapy for moderate to severe acne at all body sites, with special attention to facial involvement.

This approach is standard to acne therapy whereby mild disease will be treated with a monotherapy (i.e., 5.0% BPO) and moderate/severe disease will be treated with various combinatory regimens (topical

antibiotics, BPO, topical retinoids, oral antibiotics).

There is no precedent for topical *P. acnes* microbiome transplants in acne, but there is an analogous precedent of using autologous transplantations of coagulase-negative Staphylococcus (CoNS) species (including Staphylococcus epidermidis and Staphylococcus hominis) on 5 eczema subjects to determine their impact on colonization by *S. aureus*. In this study, CoNS species were isolated from eczema/atopic dermatitis subjects and tested for anti-staphylococcal activity against *S. aureus*. Those isolates that had antimicrobial activity against *S. aureus* were mixed in Cetaphil® (Galderma) lotion and reintroduced onto the subjects in a single application to 1 forearm at a concentration of 10^5 CFU/cm² with placebo (vehicle) applied to the contralateral forearm in a double-blinded fashion. *S. aureus* colonization was then measured 24 hours post application (Nakatsuji et al. 2017).

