Recent literature from the Human Microbiome Project has shown there are unique microbial signatures specific to healthy and acne disease states (Fitz-Gibbon et al. 2013), (Tomida et al. 2013). Subsequent literature discovered a repressor in the porphyrin pathway in health-associated strains resulting in significantly lower porphyrin production (Johnson et al. 2016). Porphyrin is a known inflammatory mediator in acne pathogenesis (Kang et al. 2015). Porphyrin levels inversely correlate with therapeutic improvement in acne. (Richter et al. 2016). Additional papers have highlighted other virulent factors such as the pIMPLE plasmid that may be associated with acne pathogenesis and were found to be more common in disease-associated strains (Kasimatis et al. 2013).

From this data, we hypothesize that by eliminating resident disease-associated bacterial strains and replacing them with a health-associated *P. acnes* transplant, we may be able to improve, mitigate, treat, or prevent acne flares. We aim to test this in an initial Phase I evaluating the safety, tolerability, and clinical impact that a single dose application of NB01 has on adult subjects with moderate acne.

This initial study will be a Phase Ib single center open label dose escalation study using a single dose application with monitoring over 28 days on 10 subjects at 2 different concentrations (lower bound and upper bound). If we meet the safety criteria of this initial study, we plan to expand the IND research to a Phase Ib multi-dosed study. All subjects will be pre-treated with a daily 5.0% BPO gel (<https://www.perrigo.com/business/product.aspx?ID=88&let=B> Perrigo 5% BP Aqueous Gel) to decrease their resident microbiome bacterial load in preparation for transplantation and successful repopulation with a healthy microbiome.

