3 OBJECTIVES AND ENDPOINTS

OBJECTIVES	ENDPOINTS	JUSTIFICATION FOR ENDPOINTS
Primary		

 Determine the safety and tolerability of a singly applied NB01 Define engraftment of a singly applied topical NB01 Dose schedule determination based on engraftment 	
Safety Assessments:
 
 Skin Dryness Skin Peeling Irritant/Contact dermatitis Hyperpigmentation Ocular Toxicity Mucosal Toxicity Skin erythema Assessment of Disease Status 
Efficacy Assessments: Engraftment is defined as deoR/PanBac>40% and Cas5/PanBac>40%. Disease associated bacteria are typically deoR, Cas5 negative (Kang et al, 2016), therefore, ratios are expected to be low <10% in acne subjects. The NB01 strain as measured with our TaqMan assays is approximately 100% deoR/PanBac and Cas5/PanBac, so we expect the ratio to increase with successful engraftment. This will help to determine dosing regimen/schedule for multi-dosed trials where the drug will be applied in a frequency to ensure that product levels remain above these parameters. For example, if deoR/PanBac drops to <40% at or before 6 hours then the application will be twice daily (BID); every (Q) 12 hours.
	Disease exacerbation along with erythema, dryness, pigmentation irritant/contact dermatitis, mucosal and ocular toxicity are commonly tested safety endpoints in topical dermatologic trials.
Secondary		
To evaluate clinical efficacy using IGA and acne lesion counts of a singly applied NB01	IGA and acne lesion count	IGA and acne lesion counts are conventional measurements for assessing efficacy in acne trials
Tertiary/Exploratory		
To evaluate biomarkers of	
 Porphyryn and sebum levels 	Porphyryn is a known

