4.3 JUSTIFICATION FOR DOSE

P. acnes is normal, commensal bacteria on the facial skin and within the facial pilosebaceous units. *P. acnes* species make up around 90% of the bacterial species on the face, irrespective of health or disease states (Fitz-Gibbon et al. 2013), (Tomida et al. 2013). In administering our live microbiome transplant topically to the face, we are delivering our health-associated *P. acnes* strains directly into their native niche, enabling optimal engraftment and thereby any beneficial effect of restoring a microbiome population to a healthy profile.

Dose Justification:

- Lower-bound dose of 10^5 CFU/cm² determined using the average within the range of normal bacterial concentration for facial skin (10^4 - 10^7 CFU/cm²) (Kishishita et al. 1980), (Akaza et al. 2016), (Nakatsuji et al. 2017) (http://www.textbookofbacteriology.net/normalflora_3.html)
- Upper-bound dose of 10^6 CFU/cm² determined by using the upper limit of normal bacterial concentration for facial skin.

Further rationale to the study design of performing topical microbiome transplants with our dose can be extracted from the methods in (Nakatsuji et al. 2017) which studied autologous microbiome transplants of 10^5 CFU/cm² CoNS in atopic dermatitis subjects.

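### Objective 3 reads NB01 persistence from a share of total bacteria alone, which cannot separate loss of product from resident recovery after BPO

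*Combined protocol and SAP*

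**What the plan says.** Section 3 gives three primary objectives. The second is to define engraftment, and the third is to settle the dose schedule from engraftment. The definition is "Engraftment is defined as deoR/PanBac>40% and Cas5/PanBac>40" (percent), and Section 4.2 repeats it. Section 4.2 also gives the two anchors: the marker ratio in acne is low, "leading to a deoR/PanBac <10% on acne individuals", and for the product "the ratios of deoR/PanBac and Cas5/PanBac is approximately 1 in our formulation".

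Both sections then carry the ratio into later trials, where "the drug will be applied in a frequency to ensure that product levels remain above these parameters". The only worked example is "if deoR/PanBac drops to <40% at or before 6 hours then the application will be BID (Q12 hours". The other strain marker, TPase2, is also reported as a ratio to PanBac.

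All subjects receive BPO "to decrease their resident microbiome bacterial load in preparation for transplantation" (Section 2.1). It ends at least 24 hours before NB01 (Section 1.2, footnote h) and is allowed only in the Screening period (Section 6.3.1). A post-BPO swab is taken immediately before application (Section 6.1.1). Section 10 is descriptive. Neither it nor Sections 3 and 4.2 give any role to the deoR, Cas5 or PanBac quantities themselves.

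**The concern.** Section 4.2 treats the ratio as a product level, but it is a proportion. Its denominator is lowered on purpose before dosing and is free to recover during the serial readings that are meant to show how long NB01 lasts. Two different histories can therefore give the same reading below 40%: NB01 has gone, or NB01 is still there and residents have grown around it. In the other direction, if BPO leaves few residents, a small remnant of NB01 can still be most of what the swab finds.

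At stake is what objective 3 can conclude. The time at which the ratio crosses 40% is to inform the schedule of the multi-dose trial. With about five subjects per cohort and descriptive analysis only, nothing else in the plan shows which of the two histories produced a fall.

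**Working it through.** The documents do not derive the 40% cut and give no power or precision figure, so there is nothing to reproduce first. The check is a two-component mixture.

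**Inputs**
- Product share carrying the marker: about 1 (Section 4.2).
- Resident share carrying the marker, b: below 10% (Section 4.2). Range used: 0 to 0.10.
- Dose D: 10^5 CFU/cm² (Cohort 1) or 10^6 CFU/cm² (Cohort 2) (Section 6.1.1).
- Normal facial load: 10^4 to 10^7 CFU/cm² (Section 4.3).
- *Assumption:* post-BPO resident load R, not stated in the documents, so a range is shown.
- *Assumption:* assay units proportional to CFU, the full dose reaching the skin, and equal swab recovery of product and residents.

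**Model.** With N the NB01 on the skin, ratio = (N + bR)/(N + R). Check: N = 0 and b = 0.10 gives 10%; R = 0 gives 100%. Both match the anchors in Section 4.2.

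**Crossing point.** Setting the ratio to 0.40 gives N = R(0.40 − b)/0.60, which is 0.67R at b = 0 and 0.50R at b = 0.10.

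**1. Product loss that still reads as engrafted**, 1 − N/D at the crossing (b = 0 to 0.10):

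| R (CFU/cm²) | Cohort 1 | Cohort 2 |
|---|---|---|
| 10^4 | 93–95% | 99.3–99.5% |
| 10^5 | 33–50% | 93–95% |
| 10^6 | cut not met even at full dose (ratio 9–18%) | 33–50% |

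**2. Resident rise that reads as loss, with no product lost.** The ratio falls below 40% once R exceeds 0.60D/(0.40 − b). That is 1.5–2.0×10^5 in Cohort 1 and 1.5–2.0×10^6 in Cohort 2. Both lie inside the 10^4–10^7 range. Section 4.3 also calls 10^6 the upper limit of normal; on that reading the Cohort 2 value lies just above it.

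**3. Same product, different reading.** Hold N at 5×10^4 with b = 0.10:
- R = 10^4: 51,000/60,000 = 85%
- R = 10^5: 60,000/150,000 = 40%
- R = 10^6: 150,000/1,050,000 = 14%

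**4. Order reversed, Cohort 1.** With 90% of the dose lost (N = 10^4) and R = 10^4, the ratio is 50–55%: engrafted. With none lost (N = 10^5) and R = 10^6, it is 9–18%: not engrafted, with ten times as much product.

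**5. Timing of the regrowth effect.** From R = 10^4, the crossing needs 15–20-fold growth in Cohort 1 and 150–200-fold in Cohort 2. Resident doubling time needed, as hours divided by log2(fold):

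| Reached by | Cohort 1 | Cohort 2 |
|---|---|---|
| 6H | 1.4–1.5 h | 0.8 h |
| 24H | 5.6–6.1 h | 3.1–3.3 h |
| 48H | 11–12 h | 6.3–6.6 h |
| Day 7 | 39–43 h | 22–23 h |

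If R starts at the dose, only 1.5–2-fold growth is needed, which by 6H means a doubling time of 6–10 h.

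**6. Why the raw marker quantity is not the answer.** In step 3, deoR quantity (N + bR) rises from 5.1×10^4 to 1.5×10^5 as R goes from 10^4 to 10^6, although N is unchanged. The resident part can be removed: since deoR = N + bR and PanBac = N + R, N = (deoR − b × PanBac)/(1 − b). At R = 10^6 this gives (150,000 − 0.10 × 1,050,000)/0.90 = 50,000, the true N.

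**The case against.** The strongest reply is that a share is the right scale for the trial's hypothesis. The aim is to replace disease-associated strains. If NB01 falls to 14% of the flora because residents have regrown, replacement has failed whatever the NB01 count. This stands for objective 2, and the ratio should remain the engraftment definition. It does not carry over to reading the ratio as an amount of product for objective 3.

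The sampling also favours a ratio. Each swab covers a different quarter of the face (Section 8.1), so per-swab quantities mix time with site and yield, while a ratio largely cancels yield. deoR and Cas5 are not specific to NB01 either, since health-associated strains carry both. Both points stand. Quantities can support the ratio but not replace it, and the resident contribution has to be removed.

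The Laboratory Manual, which is not among the documents, may set a quantification limit. Section 10.4.1 promises summaries of all variables, which could include the component quantities. A reader might infer that the study has no floor for PanBac; the documents do not establish that. They show only that the protocol names none and gives the quantities no part in the reading.

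Finally, the ratio only helps to set a later schedule, the twice-daily case is an example, and no subject's treatment in this trial depends on it. That limits the consequence.

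**Conclusion.** The point holds in a limited, conditional form. As written, objective 3 cannot tell loss of NB01 from resident recovery, and a reading above 40% does not show that most of the product is still present. The size depends on the post-BPO load, which the documents do not give: in Cohort 1 the loss still read as engrafted is 33–50% at R = 10^5 and 93–95% at R = 10^4. These figures rest on the mixture model and its stated assumptions.

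Two stronger readings are not supported. A reader might infer that near-total loss will generally pass as engraftment. Loss above 99% passes only when R is about 100 times below the dose. That is 10^4 in Cohort 2, and about 10^3 in Cohort 1, which is below the stated normal range. A reader might also infer that regrowth would drive the 6-hour example. From R = 10^4 that needs doubling times of about 1.5 h or less, so regrowth is mainly a concern at 24H and later, unless residents start near the dose.

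This is a cheap improvement to what objective 3 can conclude. It does not make the engraftment endpoint invalid.

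**What to change.** Keep both ratios above 40% as the engraftment definition. In Sections 3, 4.2 and 10.4.1, add:

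- A descriptive summary at every visit of log10 deoR, Cas5 and PanBac quantity per swab, with change from the 0H post-BPO, pre-dose swab.
- An estimated NB01 quantity, (deoR − b × PanBac)/(1 − b), where b is the subject's own 0H ratio, and the same for Cas5. State that this assumes b stays constant after 0H.
- For each fall below 40%, a statement of whether the estimated NB01 quantity fell or PanBac rose.
- Wording that no longer calls the ratio a product level.
- If the Laboratory Manual does not already do so, a rule that ratios with PanBac below the assay's quantification limit are listed as not evaluable.

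The cost is analysis wording and extra table columns. Forming the ratio already requires a signal for each target, and the 0H swab is already scheduled, so no visit, sample or subject is added. The downsides are that per-swab quantities vary with swab yield and facial quarter, so they support the ratio without replacing it, and that a few low-load swabs may become non-evaluable. Nothing here proposes a dosing frequency or a dosing rule.

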1.2 SCHEDULE OF EVENTS (SOE)

Schedule of Events (SOE) - Single Application (Phase IB): NB01-P1BSA

STUDY PERIOD ►	Baseline	Treatment						End of Study
STUDY DAY (± visit window) ►	Day -5	0H (+2 days)	6H (±2 hrs)	24H (±2 hrs)	48H (±2 hrs)	7 days (±1 day)	Unscheduled Visit ⁿ	28 days ^o (±3 days)
PROCEDURE ▼ TREATMENT DAY ►	Screening	Day 1 ^b	Day 1	Day 2	Day 3	Day 7	NA	Day 28/EOS
Eligibility Criteria Review ^a	X							
Electronic Informed Consent Process	X							
Medical History	X							
Concomitant Medication Review	X	X	X	X	X	X	X	X
Directed PE ^c	X	X					X	
Cheek Swab Engraftment Sample (TaqMan® Assay)	X ^f	X	X	X	X	X	X	X
Vital Signs ^{d, e}	X			X		X	X	X
Laboratory Assessment - CBC ^d	X						X	
Pregnancy Test (urine dipstick) ^g	X	X					X	X
BPO 5.0% gel application	X ^h							
Electronic Patient Diary	X ⁱ	X	X	X	X	X	X	X
Enrollment	X							
AE Assessment	X ^k	X ^j	X	X	X	X	X	X
Assess Porphyrin Levels (Pear 3D)	X	X	X	X	X	X	X	X
Sebum Production Measurement (Pear 3D)	X	X	X	X	X	X	X	X

Schedule of Events (SOE) - Single Application (Phase IB): NB01-P1BSA (concluded)

Skin pH measurement (Skin pH Meter)	X	X	X	X	X	X		X
Assess Follicular Engraftment via Bioré® Strip (TaqMan® Assay)	X			X				
Investigator Global Assessment (IGA)	X	X	X	X	X	X	X	X
Absolute Lesion Count	X	X	X	X	X	X	X	X
Photography (Pear 3D)	X	X	X	X	X	X	X	X
Facial Cetaphil® Washing	X ^{p,q}	X ^{l,m}	X	X	X	X	X	X
Investigator Assessment of Tolerability	X	X	X	X	X	X	X	X
Single NB01 application (by Investigator)		X						

Abbreviations: AE = Adverse Event; BID = Twice Daily; BPO = Benzoyl Peroxide; CBC = Complete Blood Counts; EOS = End of Study; PE = Physical Examination.

^a Includes confirmation of contraception use for the duration of Screening prior to first application and through study participation; Principal Investigator (PI) should assess subject eligibility after e-consent and prior to remaining screening period procedures.

^b All Day 1 baseline procedures must be completed prior to the PI application of NB01 at Time Point 0 (T0H).

^c Limited PE of face, chest, arms, back (relevant acne regions).

^d Vital signs and CBC assessed at Screening Visit, prior to initiation of BPO pre-treatment. Vital signs and CBC are only repeated if clinically warranted.

^e Blood pressure, heart rate, temperature.

^f Screening sample to be obtained prior to initiation of BPO pre-treatment.

^g Urine dipstick test, assessed locally.

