^h BPO gel should be applied for at least 5 days, in the AM immediately after the AM Cetaphil® wash. Final BPO pre-treatment should be completed at least 24 hours prior to PI application of NB01, thus final BPO application will most likely occur in the AM prior to the Day 1 (0H) visit.

ⁱ Trial subjects will note date and time of each BPO pre-treatment and Cetaphil® wash for the Screening period, and the date and time for each Cetaphil® wash during the 28-day treatment period.

^j Subjects will remain at the clinic for at least 30 minutes post application at T0H to be assessed for adverse reactions.

^k AEs will be assessed from the time of e-consent.

^l On Day 1, after baseline measurements have been obtained, subjects will then wash at the clinic before NB01 is applied by the PI.

^m Subjects initiate BID washing of their faces after waiting 24 hours from T0H, or 24H (Study Day 2). Subjects should withhold morning wash and morning facial shaving at home until they arrive at the clinic all clinic days. Once clinic day sampling has occurred, the subject may wash at the clinic. The only exception being that the subject should wash their face in the office with Cetaphil®, prior to the Day 2 Bioré® Strip follicular engraftment sampling

ⁿ Study procedures are completed as needed, as clinically indicated, for unscheduled study visits.

^o The EOS Visit should be completed on Day 28, or prior to the initiation of new anti-acne therapy. Should the subject discontinue the study early, the EOS should be scheduled and completed as soon as possible.

^p No other cleansers can be used throughout the study, from the Screening Visit to Day 28/EOS.

^q Subjects will hold the PM Cetaphil® wash prior to the Day 1 study drug application.

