6 STUDY INTERVENTION

6.1 STUDY INTERVENTION(S) ADMINISTRATION

6.1.1 DOSING AND ADMINISTRATION

There will be a single application of NB01, at 1 of 2 dose cohorts, administered to approximately 10 subjects:

Once a subject has completed BPO pre-treatment (with an in-home patient e-diary) and been enrolled into the trial, the subject will provide a post-BPO sample immediately prior to receiving their application of NB01 (hereafter referred to as “study drug”). The PI will apply a single dose of NB01 at one of two strengths to each subject at time point 0 hours (0H):

- Cohort 1: Initially, 5 subjects will be enrolled to receive a single topical application of NB01 at 10^5 CFU/cm² to 50 cm² of facial skin covering the nose and cheek. The lower-bound dose determined using the average range of normal bacterial concentration for facial skin (10^5 CFU/cm²).
- Cohort 2: If there are less than 2 DLTs in Cohort 1, then 5 subjects will have a single topical application of NB01 at 10^6 CFU/cm² to 50 cm² of facial skin covering the nose and cheek. The upper-bound dose was determined by upper limit of normal bacterial concentration for facial skin (10^6 CFU/cm²).

Investigators applying the drug shall wash their hands and wear non-powdered nitrile gloves for application of study drug material. Subjects will wash their face with Cetaphil® right after the time point 0H engraftment sample procurement and just before the study drug application. Subjects will document their BID Cetaphil® washing for the remainder of the study.

See Study Assessments and Procedures, for details on pre-and post-visit requirements during the treatment period.

See the Pharmacy Manual for additional study drug handling and management details for this study.

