8 STUDY ASSESSMENTS AND PROCEDURES

8.1 SAFETY AND OTHER ASSESSMENTS

Subjects will come to the clinic for the following protocol-specified visits: Screening, 0H (+2-day window), 6H, 24H, 48H, 7 days (± 1 -day window) and 28 days (± 3 -day window) days post application. It is important that the 6H, 24H and 48H visits be on approximately on time (± 2 -hour window) to ensure engraftment can be properly assessed.

Screening

Once the subject has provided consent to participate, the following required procedures will be completed at the Screening Visit:

- Review of subject eligibility based on inclusion and exclusion criteria
- Vitals: Blood pressure, heart rate and temperature
- Labs:
 - CBC
 - Urine dipstick pregnancy test (females of childbearing potential)
- Screening IGA score and total lesion count
- Screening porphyrin and sebum levels (Pear 3D)
- Screening photographs (Pear 3D)
- Screening pH (pH meter)
- A pre-BPO cheek swab sample will be procured
- Pre- Bioré® sampling facial wash with Cetaphil®
- A pre-BPO Bioré® sample will be obtained

The following procedures will be completed within the Screening Period:

- Subjects will initiate 5-day, at-home pre-treatment with a 5.0% BPO gel daily application to the face (<https://www.perrigo.com/business/product.aspx?ID=88&let=B> Perrigo 5% BP Aqueous Gel) at the same time each day, immediately after the AM Cetaphil® wash. The final BPO gel application should be at least 24 hours prior to study drug application (and therefore likely the morning before the Day 1 (0H) visit)
- Subjects will initiate a 5-day at-home BID Cetaphil® wash at the same time each day, with the PM wash to be held the day before the Day 1 (0H) visit. No other cleansers can be used throughout the study, from the Screening Visit to Day 28/EOS.
- Subjects will complete an in-home patient e-diary during the pre-treatment period

Once the subject's eligibility has been confirmed and pre-treatment BPO period completed, the subject will be enrolled into the study and initiate on-study procedures, including ongoing patient e-diary for Cetaphil® washes.

Treatment Period

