Post BPO-period porphyrin level, sebum production, pH, IGA assessment, total lesion count, and photos will be obtained on Day 1, followed by the engraftment assay. Urine dipstick pregnancy test will be obtained for females of childbearing potential. After these measurements are obtained, subjects will wash their face with Cetaphil® (Galderma) in the office and then the single study drug dose will be applied by the PI (OH). The application should take place at least 24 hours after the last morning BPO application. The PI will apply drug once (time point 0H) to the face: cheek/nose (approximately 50 cm²) to Cohort 1 subjects. If there are less than 2 DLTs and no possibly-related SAEs in Cohort 1 during the 7-day safety assessment, the remaining subjects will be enrolled into Cohort 2 to receive single application to the face: cheek/nose. Subjects will then be monitored for at least 30 minutes after the application for any allergic or anaphylactic reactions. Subjects should not wash or shave their face again until the 24H sampling is completed with the exception that the Bioré® strip follicular assessment will be obtained after washing face with Cetaphil® in office. Subjects may then initiate facial cleansing with Cetaphil® wash BID. However, for all office visit days, subjects should hold the morning wash and morning shaving until visit samples have been obtained.

Engraftment sample procurement: Samples for engraftment will be obtained using a Fab-Swab Filtered Air Breathable Sterile Flocked Collection Device (PurFlock® Ultra-Puritan Diagnostics). The face will be quartered into left lateral, left medial, right lateral, right medial for sampling procurement, with mid pupillary line splitting medial and lateral quarters and midline forehead/nose splitting medial quarters. Each sampling will only test a quarter of the face to ensure that sampling post drug application do not remove study drug prior to the next sampling time point and to improve standardization of sampling area. To obtain samples, the swabs should be pressed firmly and rubbed over the designated quadrant for that sample time-point with occasional rotation of the swab for a duration of a minimum of 30 seconds. Please refer to the Laboratory Manual for detailed instructions.

Subjects will be monitored for safety at all study visits: 0H, 6H, 24H, 48H, 7 days and 28 days after the initial application.

Vitals will be taken at study visits: Screening, 24H, 7 days, and 28 days.

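### The Schedule of Events marks a 6H face wash that Section 8.1 forbids; separately, the illustrative Q12h schedule example misses its own 40% aim, at least in the first interval

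*Combined protocol and SAP*

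**What the plan says.** **Washing.** The Schedule of Events has a row "Facial Cetaphil® Washing" with a mark at every visit, 6H included. Footnote m, attached to the 0H cell of that row, says "Subjects initiate BID washing of their faces after waiting 24 hours from T0H", and further on says "Once clinic day sampling has occurred, the subject may wash at the clinic". Section 8.1 says "Subjects should not wash or shave their face again until the 24H sampling is completed". Its one exception is the office wash before the Bioré strip, which after application is taken at 24H only. Section 8.1 also explains that each swab covers only a quarter of the face, so that one sample does not take away drug needed for the next.

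**Schedule.** Choosing a dosing schedule from the engraftment data is the third primary objective. Engraftment requires both deoR/PanBac and Cas5/PanBac above 40%. Sections 3 and 4.2 state that in later multi-dose trials "the drug will be applied in a frequency to ensure that product levels remain above these parameters". Both then give the same single illustration; in Section 4.2 it reads "For example, if deoR/PanBac drops to <40% at or before 6 hours then the application will be BID (Q12 hours". Section 9.1 only names the topic, and Section 10.4 gives no rule.

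**Timing.** Section 6.1.1 says "the subject will provide a post-BPO sample immediately prior to receiving their application of NB01", so the 0H swab precedes the drug and 6H is the first swab after it. Section 8.1 says "It is important that the 6H, 24H and 48H visits be on approximately on time" and allows ±2 hours.

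**The concern.** The wash conflict affects how this trial is run. The Schedule of Events is the page that site staff work from. A whole-face wash after the 6H swab would act on the quarters still to be swabbed, and so undo the protection that quarter-face sampling is meant to give. The 24H swab and the 24H strip could then read low because drug was washed off rather than because NB01 failed to persist. With about five subjects per cohort, mixed practice would be hard to detect or adjust for.

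The schedule example matters less. If it were carried into the multi-dose protocol unchanged, the finding that triggers it (level already below 40% by the first swab) would be paired with a re-application time later than that swab, although the stated purpose is to stay above 40%.

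**Working it through.** **1. Wash instructions side by side**

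| Place | Wash between application and 24H sampling? |
|---|---|
| Schedule of Events, wash row | Marked at 6H. All eight visit columns carry a mark, so this does not come from a misaligned table. |
| Footnote m, start of twice-daily washing | No, not before 24 h |
| Footnote m, clinic-wash sentence | Permissive after sampling on clinic days; 6H is not excluded |
| Section 8.1 | No |

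Footnote m names one exception, the Day 2 wash before the strip. That exception concerns 24H and does not settle 6H. The 6H cell has no footnote of its own. If a wash follows the 6H swab, the 6H reading is unaffected; the 24H swab and strip are exposed. The documents give no figure for how much drug a wash removes, so no size can be attached.

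**2. First dosing interval under Q12h**

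Inputs: threshold 40% (Sections 3 and 4.2); interval 12 h (the example); swab time t = 6 h, or 4 to 8 h with the ±2 h window (Section 8.1). Assumption: no regrowth once the ratio is below 40%.

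Hours below 40% in the first interval ≥ 12 − t:

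- t = 4: at least 8 h (8/12 = 67%)
- t = 6: at least 6 h (6/12 = 50%)
- t = 8: at least 4 h (4/12 = 33%)

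These are lower bounds, because a low first swab shows only that any crossing came earlier. If 40% was never exceeded, the figure is 12 h.

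**3. Can repeat dosing rescue Q12h?**

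The documents give no model, so one is assumed: exponential loss of NB01, constant resident load scaled to 1, equal additions every 12 h, no regrowth. Let b be the resident ratio, 0 or 0.10 (Section 3 expects below 10%), s the ratio just after the first application, and tc the time at which it crosses 40%.

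- Ratio = (N + b)/(N + 1), where N is the NB01 load
- First-dose load D = (s − b)/(1 − s); load at threshold Nt = (0.4 − b)/0.6
- Loss rate k = ln(D/Nt)/tc; steady-state peak load A = D/(1 − exp(−12k))
- Hours below 40% per 12 h = max(0, 12 − ln(A/Nt)/k)

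Example with s = 0.60, b = 0, tc = 6: D = 1.5, Nt = 0.667, k = ln(2.25)/6 = 0.135, A = 1.5/(1 − 0.198) = 1.87; hours below = 12 − ln(2.80)/0.135 = 4.4.

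Steady-state hours below 40% per 12 h (b = 0 / b = 0.10):

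| First peak s | tc = 4 h | tc = 6 h | tc = 8 h |
|---|---|---|---|
| 0.55 | 6.8 / 7.2 | 2.5 / 3.5 | 0 / 0 |
| 0.60 | 7.5 / 7.7 | 4.4 / 4.9 | 0.5 / 1.5 |
| 0.70 | 7.9 / 8.0 | 5.6 / 5.7 | 2.9 / 3.2 |
| 0.90 | 8.0 / 8.0 | 6.0 / 6.0 | 3.9 / 4.0 |

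Q12h holds 40% at steady state only if the first peak is at or below 0.469 / 0.459 (tc = 4), 0.519 / 0.502 (tc = 6) or 0.589 / 0.566 (tc = 8).

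Section 4.3 allows a rough placing. It takes 10^5 CFU/cm² as the average facial load. Assuming full delivery and no reduction by BPO, Cohort 1 has D = 10^5/10^5 = 1, so s = (1 + b)/2 = 0.50 or 0.55. With tc = 6 that gives 0 or 3.5 h below 40%. Cohort 2 has D = 10, so s = (10 + b)/11, about 0.91 or 0.92, and about 6 h. The answer depends on dose and on resident load, which Section 4.3 puts anywhere from 10^4 to 10^7 and which BPO is meant to lower.

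**The case against.** On washing: Section 8.1 is explicit, and footnote m, in the same row, starts routine washing only at 24 h. Its clinic-wash sentence follows an instruction to hold the morning wash, and most naturally concerns the order of sampling and washing. On that view the 6H mark is a clerical slip that the text already resolves. This stands in part. A careful reader would resolve it that way, but the table is itself an instruction, and nothing says which text governs. A reader might infer that subjects will be washed at 6H, or that the 24H data will be unusable. The documents support neither; they show only that the table leaves such a wash open.

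On the schedule: the text is offered as an example for later trials. No subject, sample, escalation decision or analysis here depends on it. Carry-over could rescue Q12h when the first peak is low, and NB01 is a live organism that might regrow. All of this stands. A reader might infer that Q12h leaves half of every interval below 40%, or that an interval under 6 h is needed. Neither follows. The first ignores carry-over: under the assumed model the steady-state figure runs from 0 to 8.0 h. The second ignores both carry-over and the visit window: a low swab at 4 h would call for less than 4 h, and one at 8 h only for less than 8 h. What remains is the first interval, where the shortfall needs only the no-regrowth assumption. The protocol does not cite carry-over or regrowth in support of Q12h.

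**Conclusion.** Both inconsistencies are in the current text, and the overall weight is minor.

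The wash conflict is the more important, because it can change conduct and so touch primary engraftment data at 24H. Its effect cannot be sized from the documents.

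The schedule example does not meet the aim stated just before it in the first 12-hour interval: at least 4 to 8 h below 40% for a below-40% swab taken at 8 to 4 h, assuming no regrowth. Beyond that interval the outcome depends on the first peak and the loss rate. This trial does not establish either when the first post-application swab is already below 40%, because nothing is sampled between application and that swab. The steady-state figures rest on an assumed model; they show that the answer is open, not that Q12h fails.

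**What to change.** 1. In Section 1.2, delete the 6H mark in the wash row and limit footnote m's clinic-wash sentence to visits from 24H onward. Keep the Day 2 exception for the wash before the Bioré strip. This should be done before dosing.
2. In Sections 3 and 4.2, either remove the Q12h figure, or keep it and state that some time below 40% is accepted.
3. If a bound is preferred, word it thus: when either ratio is below 40% at the first swab after application, the first re-application interval would have to be shorter than that swab's actual time, absent carry-over or regrowth; the crossing time is known only to lie before the swab, and 40% may never have been exceeded. Do not state that an interval under 6 h is needed.

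The cost is wording in Sections 1.2, 3 and 4.2, with no added visits or samples. The price of the bound is candour about a limit: when a ratio is already low at the first swab, the trial yields at most an upper bound on the interval.
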